9.0 EVALUATION OF RESPONSE TO TREATMENT

- 9.1 Evaluation of tumor extent will be recorded for the primary tumor and regional nodes at each f/u interval. PET-CT scans will be performed 12-14 weeks (+/- 1 month) after the completion of therapy to assess response.
- 9.2 Patients with any nodes who are PET-CT positive at 12-14 weeks (+/- 1 month) post cetuximab-RT may be considered for neck dissection. Patients with palpable residual nodes at 3 months whose PET-CT shows a complete response (CR) may undergo clinical observation and periodic PET scans according to the judgment of the treating clinicians.
- 9.3 Clinical examinations will be performed as comparable to clinical practice: at 1 month after the completion of therapy and then every 2 months during years 1 and 2, and at 3-month intervals during year 3, after which follow-up will be performed according to clinical practice. Allowable windows for these exams are +/- 1 month.

Clinical examinations will be performed by medical oncology, radiation oncology, and/or surgical oncology. To meet the examination requirements, patients need to be seen by at least one discipline (but not all three) during the aforementioned time intervals.

9.4 Once patients discontinue treatment (Section 13.0) or have tumor progression/recurrence, they will be followed as clinically indicated for 3 years following the completion of radiation and/or cetuximab.

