12.0 MEASUREMENT OF RESPONSE

Tumor Clearance

A patient will be considered to have a complete response if there is no measurable or palpable tumor either on clinical or radiographic (CT-PET scan) examination assessed within 3 months after the completion of treatment. Complete response will be defined as complete disappearance of disease or residual radiographic abnormality that is not considered to be tumor.

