20.2 Early Stopping Rules for Toxicity or Lack of Efficacy

In UMCC 9921 and UMCC 2-21, 2/32=6% of patients similar to those who will be treated in the current trial did not achieve tumor control. An early stopping rule will only be feasible for the identification of probability of treatment failure much higher than that. Table 1 describes the stopping rule for failure to control, which was derived using the method due to Thall, Simon and Estey [31], implemented in M.D. Anderson program multc98. **Failure is defined as local-regional recurrence or metastasis, but not second primary cancer, nor microscopic disease found in elective neck dissection, nor PET findings without correlative clinical evidence of disease persistence or recurrence.** For each number of patients enrolled, if *at least* as many failures as stated occurs (e.g., 2/5), accrual will be stopped. The rule was constructed to stop the trial if the probability that the failure rate of the experimental therapy exceeded 0.1625 (0.1 more than the historical rate) is at least 0.75.

# Patients	# Failures
5	2
10	3
15	4
20	5
25	6
30	7

Table 1 Stopping rule for failure to control tumor

Because the trial will only be stopped early for failure, and the stopping rule does not constitute an interim analysis, there will be no adjustment to the p-values of the analyses in Section 20.4.

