20.3 Analysis Plan

20.3.1 Primary Objectives

20.3.1.1 *To confirm that reducing treatment intensity in non-smoking patients with HPV-related oropharyngeal cancer does not significantly increase the proportion of patients whose tumors recur, compared to our previous experience in similar patients receiving standard-intensity chemo-RT.*

The primary index of recurrence will be the proportion of patients who have local recurrence, distant metastases or second primaries (secondary analyses will be performed on each of these endpoints individually) within two years of the end of treatment. In the primary analysis, *null* hypothesis that the proportion of patients who fail is *greater* than 0.20 will be tested using an exact binomial test (at significance level $\alpha=0.20$). The proportion of patients who recur will be calculated, with a 95% exact binomial confidence interval.

20.3.1.2 *To compare the toxicity in patients receiving reduced intensity treatment to similar patients treated with 7 weeks of chemotherapy concurrent with RT ("standard therapy") in UMCC 2-21.*

Dysphagia and mucositis are measured on continuous scales; there are both observer and patient reports. The null hypothesis of no difference in dysphagia and mucositis at three, twelve and twenty-four months posttreatment between the reduced-intensity therapy versus UMCC 2-21 will be tested ($\alpha=0.20$) in a repeated measures analysis of covariance. In addition, the statistical significance of the difference between the current trial and UMCC 2-21 in the proportions of patients experiencing clinically significant (NCI CTCAE Grade 3 or worse) toxicities will be assessed using Fisher's exact test

(a=0.20).

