20.4.2 Power of primary analysis endpoints

20.4.2.1 The ultimate goal of this research program is to conduct a randomized noninferiority trial to demonstrate that reducing the intensity of therapy in low-risk patients reduces the probability of toxicity while not increasing the probability of tumor recurrence. Such a trial will require hundreds of patients and will be possible only in the cooperative group setting. The purpose of this Phase II trial is to provide preliminary evidence that reduced intensity therapy is practical, and to provide initial evidence of efficacy and toxicity that can be used to design such a trial. The use of the relatively high significance level ($\alpha=0.2$) is not uncommon in early Phase II (e.g., Simon two-stage) trials with limited sample sizes. Out of 33 non-smoking HPV+ patients in the UMCC 2-21 reference set, three patients have died disease-free, and one patient has died from distant metastases. One additional patient in this group has developed a second primary tumor in the oral cavity. All other patients are alive and disease-free. Because the number of events is low, a time-to-event analysis is impractical, and analyses for sub-populations are also unlikely. Because the power will be modest even if the observed failure rates are 2-3 times the control rate, this trial will not definitively test that reduced intensity treatment is as effective as standard chemoradiation, but, if successful, will accrue sufficient data to motivate a true non-inferiority trial.

20.4.2 The power calculations for the toxicity endpoints (Primary Objective 2) will be represented by dysphagia, which is considered the most important. In UMCC 2-21, the patient-reported eating domain score of the HNQOL instrument increased from 10.5 ± 14.9 (mean \pm standard deviation) pre-RT to 25.7 ± 18.9 twelve months after treatment. Videofluoroscopy scores increased from 2.37 ± 1.35 pre-RT to

3.7 ± 1.18 twelve months after treatment. The power of the repeated measures analysis for Primary Objective 2 for these endpoints was assessed by Monte Carlo simulation as the mean twelve month value was reduced from the twelve-month level in UMCC 2-21 (0% decrease) to the baseline UMCC 2- 21 level (100% decrease).

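### The primary failure index in 20.3.1.1 does not name persistent disease, so a treated patient with confirmed residual tumor and no later listed event is scored as a non-failure

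*Combined protocol and SAP*

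**What the plan says.** Section 20.3.1.1 sets the primary efficacy endpoint: "The primary index of recurrence will be the proportion of patients who have local recurrence, distant metastases or second primaries", counted "within two years of the end of treatment". The test follows: the null "hypothesis that the proportion of patients who fail is *greater* than 0.20 will be tested using an exact binomial test", at a significance level of 0.20. The section gives no other definition of failing.

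Section 20.2 has its own definition for the stopping rule. The events it names are local-regional recurrence and metastasis. It then excludes second primaries, microscopic disease found in an elective neck dissection, and PET results alone: "nor PET findings without correlative clinical evidence of disease persistence or recurrence". The historical benchmark there reads "2/32=6% of patients similar to those who will be treated in the current trial did not achieve tumor control".

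Elsewhere the protocol treats failure to clear the tumor as a distinct, foreseeable outcome. Section 12.0 defines complete response as "no measurable or palpable tumor either on clinical or radiographic (CT-PET scan) examination". Section 9.2 provides for the other case, beginning "Patients with any nodes who are PET-CT positive at 12-14 weeks", and allows neck dissection to be considered. Section 7.2 plans restaging with PET-CT, endoscopy and, where judged necessary, biopsy of the tumor site. None of these results enters the primary index.

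Under Section 20.1 a patient who completes the course is evaluable, as is one whose treatment was stopped or modified for toxicity. Other patients are replaced.

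**The concern.** The first primary objective is to show that replacing chemotherapy with cetuximab does not cost tumor control. Residual tumor after treatment is the most direct form that such a cost could take, and the 12-14 week restaging is where it would first be seen. Recurrence ordinarily means return after clearance, so an index built on recurrence, metastasis and second primary has no entry for a tumor that never went away. If such a patient is salvaged by surgery, or simply has no metastasis or second primary within two years, the patient stays in the denominator and adds nothing to the numerator.

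The omission can only lower the counted failure proportion, so it favors a finding that reduced intensity is acceptable. It also leaves a judgment to be made at analysis: two analysts could score the same patient differently, one from the list in 20.3.1.1 and the other from the implication in 20.2.

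**Working it through.** **Inputs.** Null value 0.20 and significance level 0.20 (20.3.1.1); 43 enrolled to obtain 36 who complete radiation and have both biopsies (20.1); stopping boundaries of 2, 3, 4, 5, 6 and 7 failures at 5, 10, 15, 20, 25 and 30 patients (Table 1). The rate of persistent disease, q, is not in the documents; 3, 5 and 8 percentage points are assumed.

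**Step 1: the plan's own figures.** An exact sequential binomial calculation over the Table 1 looks gives probabilities of early stopping of 0.046, 0.594, 0.912, 0.992 and 0.9997 at true failure rates of 0.06, 0.2, 0.3, 0.4 and 0.5. Table 2 states 0.05, 0.59, 0.91, 0.99 and 0.99. The rule reproduces. The plan states no numerical power for the test against 0.20, so there is nothing to reproduce there.

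**Step 2: the cut-off.** The test rejects at the largest c for which P(X ≤ c | n, 0.20) ≤ 0.20.

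- n = 36: P(X ≤ 4) = 0.127 and P(X ≤ 5) = 0.246, so c = 4.
- n = 43: P(X ≤ 5) = 0.115 and P(X ≤ 6) = 0.216, so c = 5.

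At n = 36, a trial with 5 failures of which one is uncounted persistence is scored 4/36 and succeeds. Counted in full it is 5/36 and does not.

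**Step 3: effect on the error rate, ignoring early stopping.** Let true total failure be 0.20, with q of it persistence that never becomes a listed event. The counted rate is 0.20 − q, and P(success) = P(X ≤ c | n, 0.20 − q).

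| q (assumed) | Counted rate | n = 36, c = 4 | n = 43, c = 5 |
|---|---|---|---|
| 0 | 0.20 | 0.127 | 0.115 |
| 0.03 | 0.17 | 0.244 | 0.238 |
| 0.05 | 0.15 | 0.355 | 0.359 |
| 0.08 | 0.12 | 0.563 | 0.586 |

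**Step 4: with Table 1 active, n = 36.** The outcome is now the probability that accrual completes and the final test succeeds. Each patient is a listed failure (0.20 − q), a persistent case (q) or neither. Failures are assumed known at each look, with no second primaries.

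| q (assumed) | 20.2 counts persistence | 20.2 does not count it |
|---|---|---|
| 0 | 0.116 | 0.116 |
| 0.03 | 0.19 | 0.22 |
| 0.05 | 0.25 | 0.33 |
| 0.08 | 0.33 | 0.53 |

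In the second column the stopping rule weakens as well: the probability of early stopping falls from 0.594 to 0.450, 0.354 and 0.220.

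**The case against.** Four arguments go the other way.

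**The plan does not call persistence a success.** Section 20.3.1.1 leaves failing undefined beyond its list. The PET exclusion in 20.2 is needed only if clinically evident persistence would otherwise count, and Table 1 is titled as a rule for failure to control tumor. This is a fair reading of 20.2 and shows what was probably meant. It does not settle the primary index, which has its own list and no cross-reference to 20.2.

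**Not every patient whose tumor fails to clear is scored a non-failure.** A reader might infer that, and the documents do not support it. Such a patient counts if metastasis or a second primary appears within two years. One whose treatment stops for progressive disease (13.0) appears to be inevaluable under 20.1 and is replaced. The gap is confined to evaluable patients with residual disease and no later listed event.

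**The 2/32 benchmark is not shown to include tumors that never cleared.** Its tumor-control wording invites that inference. The itemized data do not bear it out: in the closely matching never-tobacco or non-smoking HPV-positive group, the Introduction reports one metastasis, one second primary and no local-regional recurrence. Section 20.4.2.1 lists three disease-free deaths, one death from metastases and one second primary, with all others alive and disease-free. No persistent case is documented. A mismatch between index and benchmark on this point is therefore unproven, and the persistence rates used above have no source in the documents.

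**The trial is exploratory.** Section 20.4.2.1 says that it will not definitively test whether the reduced treatment is as effective, and defends the loose error rate: "The use of the relatively high significance level ($\alpha=0.2$) is not uncommon in early Phase II". That lowers the severity. It does not make it acceptable for the endpoint to depend on an unstated scoring choice.

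**Conclusion.** The point holds in a limited form and should be fixed. As written, an evaluable patient with confirmed residual tumor and no later listed event within two years is a non-failure in the primary test, and Section 20.2 points the other way without saying so outright.

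One such patient can reverse the conclusion at n = 36. The effect on the error rate depends on assumed persistence of 3 to 8 points, on none of these patients having a later listed event, and on how 20.2 is applied. If 20.2 counts persistence, the chance of declaring success at a true failure rate of 0.20 rises from about 0.12 to between 0.19 and 0.33, and at 3 points it stays just below the nominal 0.20. If 20.2 does not count it, the range is 0.22 to 0.53.

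The documents do not show that persistence will occur at these rates, and the trial is not presented as definitive. It is therefore not a must-fix flaw.

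**What to change.** - In 20.3.1.1, and in the list of failure events in 20.2, add persistent disease at the primary site or in the neck, present at or after the 12-14 week restaging and dated at that evaluation. Require confirmation by pathology, or by clinical evidence that correlates with the PET finding. Pathology alone would be too narrow, because biopsy and neck dissection are discretionary in 7.2 and 9.2.
- Apply the 20.2 exclusions for microscopic disease in an elective neck dissection and for PET-only findings in both sections. Otherwise adding residual neck disease to 20.3.1.1 could count cases that 20.2 leaves out.
- Tabulate the reference patients under the same definition, without assuming that the 2/32 already contains persistent cases.

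The cost is about a sentence in each section and a recount of the reference set. No new procedure is needed, since restaging is already planned. The observed failure proportion may be slightly higher. If listed events occur at 0.0625 and persistence adds an assumed 3 or 5 points, the counted rate is 0.0925 or 0.1125, and the chance of success at n = 36 falls from 0.928 to 0.763 or 0.619. That reduction reflects failures that the index should register.

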3.0 OBJECTIVES

3.1 Primary Objectives

- 3.1.1 To confirm that reducing treatment intensity in patients with HPV related oropharyngeal cancer and ≤ 10 pack-year smoking history by replacing concurrent chemotherapy with concurrent cetuximab, does not significantly increase the proportion of patients whose tumors recur, compared to our previous experience in similar patients receiving chemo-RT.
- 3.1.2 To compare the toxicity in patients receiving cetuximab-RT to similar patients treated with 7 weeks of chemotherapy concurrent with RT ("standard therapy") in UMCC 2-21.

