20.0 STATISTICAL CONSIDERATIONS

20.1 Study Design

This is a Phase II trial of seven weeks RT+cetuximab for head and neck cancer in patients with good prognoses to determine if this treatment will be at least as effective as, but less toxic than, standard therapy. A total of 43 patients will be enrolled in order to obtain 36 patients that complete radiation treatment and have both biopsies taken. Thus, both the clinical primary endpoints and scientific secondary endpoints can be analyzed, as EGFR tumor information is useful for determining potential mechanisms of resistance to cetuximab. Based on the experience of UMCC 9921 and UMCC 2-21, accrual is expected to average one patient per month. To be considered evaluable, a patient must complete the full course of radiation/cetuximab. If radiation and/or cetuximab was stopped or modified due to toxicity, the patient is still evaluable. Inevaluable patients will be replaced.

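### The primary recurrence test can show only that two-year failure is below 20%, so a pass cannot confirm that recurrence is not increased or that treatment is at least as effective

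*Combined protocol and SAP*

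**What the plan says.** Section 3.1.1 sets out to confirm that replacing chemotherapy with cetuximab "does not significantly increase the proportion of patients whose tumors recur, compared to our previous experience in similar patients receiving chemo-RT". Section 20.1 gives the trial's purpose as "to determine if this treatment will be at least as effective as, but less toxic than, standard therapy". Section 20.3.1.1 repeats the objective and defines the index as the proportion of patients with local recurrence, distant metastases or second primaries within two years of the end of treatment. The null hypothesis is that this proportion is greater "than 0.20 will be tested using an exact binomial test", at alpha 0.20, and a 95% exact interval is also reported.

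The historical figures appear elsewhere. Section 20.2 says that "2/32=6% of patients similar to those who will be treated in the current trial did not achieve tumor control" and builds the stopping rule on a posterior probability that the "failure rate of the experimental therapy exceeded 0.1625 (0.1 more than the historical rate) is at least 0.75". Its definition of failure leaves out second primaries. Section 20.4.2.1 describes 33 non-smoking HPV-positive reference patients: one died of distant metastases, one developed a second primary, and three died disease-free. The same section says that the trial will not be a definitive test of equal efficacy and is meant to give preliminary evidence for a later non-inferiority trial. It calls the power modest but gives no cut-off and no power figure for the recurrence test.

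**The concern.** The objective is a comparison with past experience, whereas the test compares the trial with a fixed 0.20. Rejecting that null says that failure is below 20%. It does not say that failure is no higher than about 6%, and the plan gives no reason why 20% should stand in for no increase. A reader who takes the objective at its word would treat a pass as evidence that de-escalation is safe for tumour control. These patients have an excellent prognosis on standard treatment, and the result is meant to motivate a randomised non-inferiority trial, so what a pass shows needs to be stated accurately.

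**Working it through.** **Inputs.** Null 0.20 and alpha 0.20, one-sided in effect (20.3.1.1). Reference events 2/33 (20.4.2.1) and 2/32 (20.2). Stopping boundaries of 2, 3, 4, 5, 6 and 7 failures at 5, 10, 15, 20, 25 and 30 patients (Table 1). For sample size, 20.1 states: "A total of 43 patients will be enrolled in order to obtain 36 patients that complete radiation treatment and have both biopsies taken". The main case below takes n = 36, with n = 43 alongside.

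**The plan's own figures.** The documents give no operating characteristic for the 0.20 test, so the nearest figure to reproduce is Table 2. An exact binomial recursion over the Table 1 boundaries gives these probabilities of stopping early:

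| True rate | Recomputed | Table 2 |
|---|---|---|
| 0.06 | 0.046 | 0.05 |
| 0.2 | 0.594 | 0.59 |
| 0.3 | 0.912 | 0.91 |
| 0.4 | 0.992 | 0.99 |
| 0.5 | 1.000 | 0.99 |

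The stopping rule therefore reproduces, and the same recursion is used below.

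**Null against history.** On the primary index's event list the reference set has 1 metastasis + 1 second primary = 2 events in 33, or 6.1%. The ratio is 0.20 / (2/33) = 3.3. With 2/32 = 6.25% it is 0.20 / 0.0625 = 3.2. The exact 95% CI is 0.7% to 20.2% for 2/33 and 0.8% to 20.8% for 2/32.

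**Cut-off.** This is the largest c with P(X ≤ c | n, 0.20) ≤ 0.20.
- n = 36: P(X ≤ 4) = 0.127 and P(X ≤ 5) = 0.246, so a pass is 4 or fewer failures (4/36 = 11.1%) and the attained size is 0.127.
- n = 43: P(X ≤ 5) = 0.115 and P(X ≤ 6) = 0.216, so a pass is 5 or fewer failures.

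**What a borderline pass shows.** At 4/36 the one-sided 80% upper limit is 18.0% and the exact 95% CI is 3.1% to 26.1%.

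**Chance of a pass.** The final test alone is P(X ≤ c | n, p). The second figure in each cell also requires that no Table 1 boundary was met, with the two failure definitions treated as one.

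| True failure rate | n = 36: test alone / with stopping rule | n = 43: test alone / with stopping rule |
|---|---|---|
| 6% | 0.94 / 0.91 | 0.96 / 0.92 |
| 12% (double 6%) | 0.56 / 0.53 | 0.59 / 0.54 |
| 12.5% (double 6.25%) | 0.53 / 0.49 | 0.55 / 0.50 |
| 18% (triple 6%) | 0.20 / 0.18 | 0.19 / 0.17 |
| 20% | 0.13 / 0.12 | 0.11 / 0.10 |

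The figures with the stopping rule are the low end. Second primaries count in the final test but not toward stopping, so the true joint probability lies between the two figures in each cell.

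**The case against.** The strongest reply is that the plan already admits the limitation. Section 20.4.2.1 says that equal efficacy will not be definitively tested, calls the evidence preliminary, and defends alpha 0.20 as common in early phase II. That is a fair description of the design. It does not remove the mismatch, because the objective and the design statement still claim more, and the reader is given no cut-off from which to see that 4/36 counts as success.

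Second, the 6% rests on two events, and the reference patients in 20.4.2.1 are non-smokers, while 7.2 admits patients with up to 10 pack-years. The expected rate here may be higher, so the ratio of about 3 is soft. This is accepted. It could help to justify 0.20, but the plan does not offer it as a reason.

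Three stronger readings are tempting and are not supported:
- A reader might infer that a doubled rate has a better than even chance of passing. That holds for the final test alone. With the stopping rule it is about even.
- A reader might infer that 0.20 breaches the plan's own limit of 0.1625. Section 20.2 says "The rule was constructed to stop the trial if the probability that the failure rate of the experimental therapy exceeded 0.1625" with at least 0.75 posterior probability. That is a Bayesian stopping threshold, not a margin, and its failure definition excludes second primaries. A broader endpoint can carry a higher limit.
- A reader might infer that the 95% CI contradicts the test, since at 4/36 it contains 0.20. A two-sided 95% interval and a one-sided test at the 0.20 level answer different questions and may differ.

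**Conclusion.** The concern stands as a mismatch between claim and test, and it should be corrected. A pass supports the statement that two-year failure is below 20% at a one-sided 0.20 level. It does not support a claim of no increase over about 6%, or of being at least as effective. A true doubling of failure would pass about half the time: 49% to 56% with 36 patients and 50% to 59% with 43, depending on whether doubling means 12% or 12.5% and whether the stopping rule is counted.

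These figures assume that all 36 or 43 patients are assessable at two years. The doubling is taken from the observed historical rate, although 20.4.2.1 does not say over what period the reference events were counted. The test itself is not invalid, and alpha 0.20 is not at issue.

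**What to change.** In 3.1.1, 20.1 and 20.3.1.1, define success as preliminary evidence that the two-year failure rate is below 20%. Drop the claims of confirming no increase and of being at least as effective, so that these sections agree with 20.4.2.1. In 20.3.1.1 or 20.4.2.1, state the cut-off (4 or fewer of 36, or the equivalent for the number analysed) and its operating characteristics, and give the reason for 0.20 in light of the 6% historical rate. All of this is wording; sample size and analysis do not change.

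Optional: report the one-sided 80% upper limit, which matches the test, beside the 95% interval.

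Not required: changing the null to 0.1625. With 36 patients a pass would then be 3 or fewer failures (attained size 0.142). The chance of passing would fall from 0.53 to 0.33 at 12.5%, and from 0.94 to 0.83 at 6%. That is a design trade-off. It would move a threshold built for a different failure definition onto this endpoint, and it still could not show that there is no increase.

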2.0 STUDY HYPOTHESIS AND RATIONALE

Taking into account the excellent prognosis of patients with HPV-positive oropharyngeal cancer with ≤ 10 pack-year smoking, we hypothesize that reducing the intensity of therapy for these patients will reduce treatment sequelae, notably long-term dysphagia, without affecting their cure rates. The main Aim is to assess whether reducing treatment intensity, by replacing concurrent chemotherapy with cetuximab, will indeed achieve improved long-term toxicity. This Aim will be tested in a prospective study in which acute and long-term sequelae will be graded by observers (using CTCAE v4.0) and by patients (via HN-specific QOL questionnaires). Dysphagia will also be assessed objectively by videofluoroscopy. These measures will be compared to our historical control group (consisting of non-smoking patients with advanced oropharyngeal cancer who received standard-intensity chemo-RT and were evaluated by the same tools on UMCC protocol 2-21). Strict stopping rules will be enacted to ensure that reducing treatment intensity does not increase tumor failures compared with our previous results using standard therapy.

EGFR expression and down-stream signaling will be tested before and after the loading dose of cetuximab (before radiotherapy starts). We hypothesize that in this population with good prognosis, EGFR downstream inhibition after cetuximab test dose will be achieved in the large majority of patients, and that these characteristics will differ significantly from the characteristics of EGFR inhibition which will be observed in poor-prognosis oropharyngeal patients who smoke and/or have HPV- tumors. (These patients will be treated on a different, parallel protocol in which the intensity of therapy will be increased and in whom EGFR level will also be examined before and after a loading dose of cetuximab.)

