4.0 INCLUSION CRITERIA

- 4.1 Patients must have pathologically-confirmed, previously untreated, stage III-IV(excluding N3 or T4) squamous cell carcinoma of the oropharynx, without evidence

of distant metastasis

4.2 Pretreatment tumor biopsy with sufficient tumor for HPV or p16 analysis is required. The tumor must be HPV(+) or p16(+)

4.3 Smoking history <10 pack-year or equivalent (including cigarettes, cigars, pipes, chewing tobacco, and/or marijuana.) One cannabis joint is equivalent to 5 cigarettes. (Aldington et al, Thorax 2007; 62:1058-1063)

Smoking status definitions (National Health Interview Survey and Behavioral Risk Factor Surveillance System (Nelson DE et al, Am J Pub Health 2003;93:1335):

- Smokers: smoking now every day or some days in past month
- Quitters: at least 100 cigarettes/lifetime and not smoking in the past 1-12 months
- Former smoker: at least 100 cigarettes/lifetime and not smoking >12 months
- Never smokers: <100 cigarettes (or equivalent)/lifetime

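### The primary toxicity comparison describes its UMCC 2-21 controls more broadly than this trial's eligibility, and the only test that names mucositis starts three months after treatment, although the excess is described as acute

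*Combined protocol and SAP*

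**What the plan says.** Section 3.1.2 makes toxicity a primary objective: "To compare the toxicity in patients receiving cetuximab-RT to similar patients treated with 7 weeks of chemotherapy" concurrent with RT in UMCC 2-21. Section 20.3.1.2 repeats the word similar without defining it. Section 2.0 gives the only description written for the toxicity controls: a group "consisting of non-smoking patients with advanced oropharyngeal cancer who received standard-intensity chemo-RT" and was assessed with the same tools.

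The trial's own population is narrower. Section 4.1 requires "stage III-IV(excluding N3 or T4) squamous cell carcinoma of the oropharynx". Section 4.2 states "The tumor must be HPV(+) or p16" positive. Section 4.3 sets "Smoking history <10 pack-year or equivalent".

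Section 20.3.1.2 plans two kinds of test, each at alpha 0.20:

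- a repeated-measures analysis of covariance of "The null hypothesis of no difference in dysphagia and mucositis at three, twelve and twenty-four months posttreatment", with covariates not named;
- a Fisher test of the difference "in the proportions of patients experiencing clinically significant (NCI CTCAE Grade 3 or worse) toxicities", with no time window.

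On acute effects, section 1.0 names acute mucositis as a main added toxicity of concurrent chemoradiotherapy. Section 2.0 says "acute and long-term sequelae will be graded by observers (using CTCAE v4.0") and by patients, and that these measures will be compared with the historical controls. Section 10.1 has CTCAE items gathered weekly on treatment and at every follow-up visit to 3 years.

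**The concern.** **Controls.** With a historical comparator, any difference in who was treated enters the estimate together with the change from chemotherapy to cetuximab. Read as written, section 2.0 would admit T4 or N3 controls, whom this trial excludes. There is a reason in the documents to care about stage. Section 1.0 reports that dysphagia correlated with dose to the swallowing structures, and section 8.2.3 minimises dose to those structures only outside the targets. That T4 or N3 targets would leave less to spare is my inference; the protocol does not say it.

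**Mucositis.** If the excess is acute, a test starting at three months looks after much of it may have passed. The Fisher test could capture on-treatment events, but without a window it could be run on acute events, late events or both, and the choice could be made after the data are seen. The trial could then report on mucositis without a prespecified comparison in the period the protocol itself singles out.

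**Working it through.** **1. Control description against eligibility**

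| Criterion | This trial (section 4.0) | Toxicity controls (section 2.0) |
|---|---|---|
| HPV/p16 | positive required | not stated |
| T and N | T4 and N3 excluded | advanced; no T/N limit stated |
| Tobacco | under 10 pack-years | non-smoking, not defined there |

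T/N is the main open item. The background series in section 1.0 is described as stage III or IV with no T4/N3 exclusion stated. HPV is a smaller gap: in that series all 22 HPV-negative patients had used tobacco, so if non-smoking means never-users it would have removed them. The tobacco wording may simply be loose, because section 20.3.1.1 also calls the trial's own population non-smoking.

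**2. Control numbers**

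Section 20.4.2.1 gives 33 non-smoking HPV-positive patients in the UMCC 2-21 reference set, in a paragraph about recurrence and death. Section 20.2 counts 32 similar patients over UMCC 9921 and UMCC 2-21 together. The videofluoroscopy (VF) and HNQOL means in section 20.4.2 carry no n.

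**3. The plan's power figure**

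Inputs: VF score 2.37 before RT and 3.7 (SD 1.18) at twelve months (section 20.4.2); at least 80% power at a 58% decrease (section 20.4.3); 36 trial patients (section 20.1); alpha 0.20 (section 20.3.1.2).

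- Effect = 0.58 × (3.7 − 2.37) = 0.58 × 1.33 = 0.771 points.
- With 33 controls, SE = 1.18 × √(1/36 + 1/33) = 0.284, and 0.771/0.284 = 2.71. Two-sided power by noncentral t (67 df) = 0.92.

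This agrees with at least 80%. The plan's simulation cannot be reproduced exactly, because control n, within-patient correlation and sidedness are not given.

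**4. What restricting the controls would cost**

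Same model: a 12-month two-group comparison, 36 trial patients, two-sided alpha 0.20. The last column assumes a baseline-to-12-month correlation of 0.5, so SD = 1.18 × √(1 − 0.25) = 1.022.

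| Controls | Power, unadjusted | Power, baseline-adjusted (r = 0.5) |
|---|---|---|
| 33 | 0.92 | 0.97 |
| 20 | 0.85 | 0.92 |
| 16 | 0.81 | 0.89 |
| 10 | 0.70 | 0.79 |

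The smallest control group giving 80% is 16 unadjusted and 11 adjusted. With 30 trial patients at twelve months, these become 17 and 12. The result depends on the model. If change scores were analysed with a correlation of 0.3, SD = √(1.18² + 1.35² − 2 × 0.3 × 1.18 × 1.35) = 1.50, and power with 33 controls is about 0.80, which leaves no room to shrink.

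**5. Mucositis timing**

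The toxicity is described as acute (1.0), acute sequelae are to be compared (2.0) and CTCAE grades are collected weekly on treatment (10.1). The one test naming mucositis uses 3, 12 and 24 months (20.3.1.2). The data for an acute comparison will exist in this trial; the plan does not fix one. The documents give no mucositis rates, so I offer no size.

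**The case against.** The best reply is that similar has context. Section 3.1.1 introduces similar patients straight after naming HPV-related disease and at most 10 pack-years. The last part of section 1.0 lists the low-risk criteria, including below T4 and below N3, and then promises comparison with past chemo-RT patients. The reference figure in section 20.4.2.1 is HPV-positive. This makes HPV and smoking weak complaints, and the sponsor may already intend a matched group. None of it is a selection rule for toxicity, and the T4/N3 point stands as a gap in the text, although it is an argument from silence.

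It is also fair that this is a phase II trial meant to inform a randomised one, and that an extra mucositis test joins several unadjusted tests under one objective. That supports a small, clearly specified addition.

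Four stronger readings are tempting and are not supported:

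- *The comparison is biased towards cetuximab.* No T/N mix is given for either cohort, so neither size nor direction can be stated.
- *The plan gives no control number.* It gives 33; what is missing is a number tied to the toxicity scores.
- *The power claim fails.* With 33 controls it holds under the simple model.
- *Late toxicity is recorded only if judged related.* Section 17.0 limits late adverse-event reporting in that way, but sections 10.1 and 11.0 collect CTCAE toxicity at every visit through 3 years. The missing Fisher window stands without this argument.

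**Conclusion.** The concern holds in two limited respects. First, the stated description of the toxicity controls is broader than the trial's eligibility, chiefly on T4/N3, so case mix can enter a non-randomised primary contrast by an unknown amount in an unknown direction. Second, no prespecified test is fixed on the acute period for mucositis, although the protocol calls that toxicity acute and says acute sequelae will be compared.

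The unnamed covariates, and the lack of an n beside the VF and HNQOL means, are missing detail and do not show a wrong result. The threshold of about 16 controls rests on a single 12-month comparison, SD 1.18, 36 trial patients and two-sided alpha 0.20, and it stands in for a simulation that is not reported. This is worth changing before analysis; it does not invalidate the design.

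**What to change.** **Controls.** Define the toxicity controls as UMCC 2-21 patients who meet this trial's HPV/p16, T/N and pack-year criteria, as far as the records allow, and state how many there are. The pack-year limit is written as under 10 in section 4.3 and as at most 10 in sections 3.1.1 and 7.2; reconcile these before using it to select controls. Adjust the repeated-measures analysis for baseline score, and for T/N category only where restriction is not possible.

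Cost: plan wording and re-selection of existing records. The control group may shrink. Restate the power if fewer than about 16 controls remain, or if the analysis model differs from the simple one above.

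**Mucositis.** Keep all planned analyses. Prespecify one comparison of worst CTCAE mucositis grade from the start of RT to 1 month after RT, using an ordinal test. If UMCC 2-21 holds only Grade 3 or worse, use the planned Fisher test in that window. For the Fisher test generally, fix an acute and a late window, apply both identically to the two cohorts, and list the toxicities.

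Cost: one added comparison, whose place among the primary toxicity tests should be stated. It depends on UMCC 2-21 holding on-treatment grades, which must be confirmed. This trial needs no new data collection.
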